For *static aspiration*, the VacLok syringe is opened to create suction on the clot for a minimum of one minute (some interventionalists may prefer a longer 'dwell time' to encourage more clot ingestion, which is fine). Once the syringe is locked open, a timer is used to ensure adequate timekeeping. Once at least 1 minute or more has passed, then the catheter is carefully withdrawn into the guide catheter and removed. The guide catheter is then thoroughly aspirated to clear any fragmented clot. The duration of aspiration will be reported on the case report form (CRF). Other syringes or devices for aspiration may be introduced during the trial at the discretion of the steering committee.

Plunger Technique

The VacLok syringe is also used for the Plunger technique. The catheter is navigated to the clot face and aspiration is applied by drawing the syringe plunger back. However, the syringe is not locked, but instead the plunger is repeatedly pulled back and then released in a cyclic fashion [[Froehler, JNIS 2023](#)]. There is no need to cycle slowly, as seen in the how-to video. Operators may wish to pull the plunger more quickly than it is released, though our *in vitro* studies have shown that there is always negative pressure at the catheter tip and therefore no risk of 'pushing' the clot. Although obvious, it is important to note that when the plunger is released it should not be actively pushed forward as this could push the clot out of the catheter and into the distal vasculature.

When using the Plunger technique in the trial, active plunging must be performed for at least 30 s at a time, with pauses of no more than 30 s. When paused, the syringe must be locked in the fully open / full vacuum position. Total aspiration time, including active plunging and static vacuum pauses, must be at least one minute (one cycle of plunging). As with static aspiration, some surgeons may prefer to use a longer total aspiration time, which is acceptable. The VacLok syringe must then be locked in the full vacuum position before the catheter is removed in a fashion identical to that described above for the static aspiration technique.

Rescue treatment

Rescue therapy may be provided to the subject at the discretion of the study investigator. In the event that aspiration thrombectomy fails to achieve successful reperfusion (defined as TICI \geq 2b) after at least one attempt, any other FDA-approved thrombectomy device may be used by the study physician.

Training

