- Rate of recanalization by clot density on CT (hyperdense vs isodense). There is evidence that hyperdense clot contains a higher fraction of red blood cells, is softer, and is more readily removed with thrombectomy devices. This has not been assessed in aspiration thrombectomy.

Risk Assessment

- This study poses no more than minimal risk to participants. All subjects will undergo a standard mechanical thrombectomy procedure, with the only difference being the method of aspiration; either static or cyclic (Plunger) technique. Both techniques are widely used in clinical practice, are considered standard of care, and have comparable safety profiles. No investigational devices or procedures will be used. As such, participation in the study does not expose subjects to risks beyond those encountered in routine clinical care.

Investigational plan

Trial design

The Plunger trial is a prospective, multicenter, randomized, controlled trial of the Plunger technique vs. static manual direct aspiration thrombectomy to assess recanalization efficacy for treatment of acute large vessel occlusion stroke. Participants will have a large vessel occlusion in the anterior circulation of the terminal ICA or M1 segment of the MCA.

Ethical Considerations and Informed consent

This study compares two suction techniques: static aspiration and the cyclic aspiration (plunger technique) both of which are standard practices in mechanical thrombectomy. These techniques are routinely employed by physicians based on individual preference and training. All procedures involved are part of routine clinical care and utilize FDA-cleared devices (e.g., Raptor catheters and 60cc VacLok syringes). No investigational devices or experimental procedures are introduced. Importantly, both techniques have similar/identical risk profiles, as they are commonly used in clinical practice and do not introduce additional risks beyond those encountered in standard stroke treatment. Therefore, this study meets the definition of minimal risk research under federal regulations.

Informed consent process:

The patient consent process will be conducted using a REDCap-based electronic consent form. The consent form has been developed in REDCap, a secure, web-based, HIPAA-compliant, data collection platform with a user management system allowing project owners to grant and control varying levels of access to data collection instruments and data (e.g. read only, de-identified-only data views) for other users.

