An Adverse Event (AE) is any untoward medical occurrence, unintended disease or injury, or untoward clinical signs (including abnormal laboratory findings) in subjects, users or other persons, whether or not related to the investigational procedure.

A Serious Adverse Event (SAE) is an AE that:

- Led to death
- Led to a serious deterioration in the health of a patient that:
 - 1) Resulted in a life-threatening illness or injury
 - 2) Resulted in a permanent impairment of a body function or body structure
 - 3) Required in-patient hospitalization or prolonged hospitalization
- Resulted in medical or surgical intervention to prevent permanent impairment to a body function or body structure
- Led to fetal distress, fetal death or a congenital abnormality or birth defect.

For the current study, detailed and narrative reports of the following specific adverse events will be obtained:

- Incidence of death 24 hours post procedure
- Vessel perforation
- Vessel dissection
- Failure to navigate to target

Adverse Event Assessments

Relatedness:

- Procedure-related: Event has a strong temporal relationship to the study procedure. This includes AEs attributable to any device(s) used at procedure, such as access devices, delivery microcatheters, non-ionic contrast, guidewires, or any other adjunctive, approved/cleared device for neurovascular procedures.
- Technique-related: Event has a strong temporal relationship to the use of aspiration for thrombectomy.
- Unknown: Event relationship cannot be attributed to any of the above categories and remains undetermined.

Event Reporting Requirements

Any adverse event that occurs during the course of the study must be recorded and reported using the appropriate Adverse Event eCRF. These will include events occurring from the point of consent until a subject exits the study. The Investigator must sign each AE eCRF report. Investigators must obtain all information available to determine the causality and outcome of the AE and to assess whether it meets the criteria for classification as serious and the relationship of each adverse event to the procedure or device.

Pre-existing medical conditions or symptoms occurring prior to the start of the procedure should not be reported as adverse events. In the situation where there is a worsening of a pre-existing medical condition or symptom due to a study related procedure, an adverse event should be reported.

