The Investigator is required to report all SAEs within 72 hours after first learning of the event. The primary method of reporting SAEs will be through the eCRFs. All SAEs will also be reported to the local IRB.

Site selection

Potential clinical sites will be assessed to ensure the investigator and his/her staff have the facilities, expertise required for the study and ability to conduct the study according to the clinical protocol.

To participate in this trial a clinical site must have, at a minimum, the following:

- 24/7 stroke interventional capabilities
- CT-based acute stroke imaging protocols (MRI is not acceptable)
- Ability to support timely data collection via an Internet-based EDC system
- Resources for conducting the informed consent process
- Willingness to adhere to the study protocol

Angiographic core lab

The procedural angiograms will be submitted by each site with all subject identifiers removed and only the assigned subject study number on the images. Each angiogram will be blindly assessed by the core lab for:

- Reperfusion score after first pass
- Reperfusion after final aspiration pass
- Reperfusion at end of procedure

Oculus Imaging, LLC, will serve as the core lab. The core lab services will include:

1. Trial Specific Website Design

- a. We will customize a user accessible website on our server specifically for the requested study. All imaging aspects of the study will be managed through this site.
- b. The primary functions of the site include electronic image submission, de-identification, and analysis.
- c. The website may also allow users or sponsors to review subject images and the dynamic trial reports as needed.
- d. Our study websites are secure, HIPAA, FDA, (CFR part 11) and E-Union compliant. Daily backups are performed.
- e. Studies are stored in at least two separate off-site archive sites.
- f. After launch of the trial website, any requested changes to the data collection for this trial may require a database change. Such requests would be reflected in a new version of the trial guidelines. Database changes may require revalidation of the trial imaging reports and additional fees may apply.

2. Imaging Protocol

- a. Oculus Imaging will write the Imaging Guidelines detailing imaging modalities to be used, imaging acquisition protocols, and procedures for image transfer.

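### Distal or new-territory embolization, a hazard the protocol links to misuse of the Plunger manoeuvre, is neither defined nor solicited nor read blind, so any between-arm comparison would rest on unsolicited reports from unblinded operators.

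*Protocol*

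**What the plan says.** **The hazard.** Under Plunger Technique, the protocol gives this warning about the syringe plunger in the release phase: "it should not be actively pushed forward as this could push the clot out of the catheter and into the distal vasculature". The sentence before it qualifies this: citing the investigators' in vitro studies, it says "there is always negative pressure at the catheter tip and therefore no risk of" pushing the clot. The hazard is therefore tied to active pushing, which operators are told to avoid.

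**What is solicited.** Adverse Event Classification and Definitions states: "For the current study, detailed and narrative reports of the following specific adverse events will be obtained". Four items follow: death by 24 hours, vessel perforation, vessel dissection, and "Failure to navigate to target".

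**What is read blind.** The Angiographic core lab section says "Each angiogram will be blindly assessed by the core lab for" three things. The first is "Reperfusion score after first pass"; the others are reperfusion after the last aspiration pass and at the end of the procedure. Item 2b of that section leaves the final data points to Reading Guidelines that the sponsor has still to approve.

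**What else bears on it.** The Adverse events section and Event Reporting Requirements make recording of any adverse event mandatory, with its relation to technique, device and procedure. The Study objective is to compare efficacy and safety. Risk Assessment says that the two techniques "are considered standard of care, and have comparable safety profiles".

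**The concern.** The protocol sets out to compare safety and describes one way in which clot could be driven downstream by a step that only one arm performs repeatedly. In the static arm the syringe is locked open. An investigator following the document would expect a field for this event, and there is none.

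The event matters in both directions. The Background cites, as preliminary evidence for cyclic pumps, a study whose title in the reference list claims less distal embolization. The protocol thus warns of a possible harm and leans on a possible benefit concerning the same outcome, with no dedicated measure of either.

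At stake is how far the trial can support its statement on comparable safety, and what the DSMB would be shown. The primary efficacy and sICH analyses are not affected.

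**Working it through.** **1. Search of every place where the event could be captured.**

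| Place in the protocol | What it holds | Embolization item? |
|---|---|---|
| Primary safety endpoint | sICH at 24 hours | No |
| Secondary endpoints | TICI, mRS, navigation, rescue, ingestion, catheter size, clot density | No |
| Data collection, procedure data | TICI after each pass (site), clot ingestion, times, devices, rescue | No |
| Data collection, 24-hour data | Hemorrhage, sICH, NIHSS | No |
| Specific adverse events | Four events, none embolic | No |
| Core-lab read | Three reperfusion scores | No |
| General adverse-event reporting | Any untoward event, with relatedness | Yes, but unsolicited and undefined |

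**2. What the remaining routes deliver.**

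- *General reporting.* The operator knows the assigned technique, there is no definition to apply and no field that prompts for the event. The technique-related category refers to aspiration as such. It applies to both arms and does not isolate the Plunger manoeuvre.
- *TICI.* Clot lost within the target territory lowers the grade, so an excess in one arm would show indirectly, including in the primary endpoint. A lower grade may equally mean residual clot. An embolus in another territory is not recorded.

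**3. Illustrative size.** The protocol states no embolization rate, so there is no planned figure to reproduce. All rates below are assumptions. Arm sizes are 500/2 = 250 and, for the stated minimum, 462/2 = 231.

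Power for two proportions, two-sided 0.05, n per arm:

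power = Φ[(|p₂ − p₁| − 1.96·SE₀)/SE₁], with SE₀ = √[2p̄(1 − p̄)/n] and SE₁ = √{[p₁(1 − p₁) + p₂(1 − p₂)]/n}.

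For 5% vs 12% and n = 250: p̄ = 0.085, SE₀ = 0.0249, SE₁ = 0.0247. Then (0.07 − 0.0489)/0.0247 = 0.853, and Φ(0.853) = 0.80.

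| Share of events reported, both arms | Reported rates | Power, 250 per arm |
|---|---|---|
| 100% | 5.0% vs 12.0% | 80% |
| 50% | 2.5% vs 6.0% | 49% |
| 30% | 1.5% vs 3.6% | 32% |

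Unequal reporting also biases the estimate. If static operators reported 50% and Plunger operators 30%, true rates of 5% and 12% would appear as 0.50 × 5 = 2.5% and 0.30 × 12 = 3.6%. A 7-point difference would shrink to 1.1 points.

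**4. What complete ascertainment could show.** At 80% power and an assumed 5% static rate, the smallest detectable Plunger rate is about 12.0% with 250 per arm and 12.3% with 231. Over static rates of 2% to 10% and both arm sizes, the detectable increase runs from about 5.3 to 9.2 points. For precision in one arm, rates of 3% to 8% mean roughly 8 to 20 events in 250, with exact 95% intervals of 1.4% to 6.2% (8/250) and 5.0% to 12.1% (20/250).

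**The case against.** The strongest reply is that the event is already covered. Recording of adverse events is mandatory, not optional, and the list of four only marks which events need a narrative; it does not limit capture. Reported emboli can therefore be tabulated by arm and shown to the DSMB. This stands. A reader might infer from the missing field that the trial cannot compare embolization between arms, or that nothing at all would be ascertained. The documents do not support that.

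Second, the hazard belongs to departure from the technique, and the protocol says that correct release carries no risk. This also stands as a reading of the text, and no passage says that embolization is the harm most likely to differ between arms. But the reassurance is in vitro, the clinical experience described is from one center, and the trial plans 20 sites. Because patients are compared as randomized once navigation failures are excluded, errors of execution are part of what the trial estimates.

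Third, TICI is read blind and would count downstream clot against the arm that caused it. This is true for the target territory, with the limits given above.

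Fourth, the Reading Guidelines and CRFs are not shown and may include the item. They may. The protocol nevertheless lists what the core lab will assess, and embolization is not on that list.

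Finally, a dedicated field would still detect only large differences. That is correct, and it is why the outcome should be descriptive.

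**Conclusion.** The point holds as a gap in definition and ascertainment. It contradicts nothing in the protocol and leaves both primary analyses intact. The protocol names a route by which clot could reach the distal vessels and makes safety a comparative objective, yet it neither defines distal or new-territory embolization nor solicits it, and its listed blinded read does not include it. What remains are unsolicited reports from unblinded operators and an indirect signal in TICI.

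The size cannot be derived from the documents. The rates of 3% to 8% and 5% vs 12%, and the reporting shares of 50% and 30%, are assumptions with no source in the protocol. They show only that under-reporting would weaken the comparison, and that unequal reporting could hide or create a difference. The absence of the field is plain in the text and does not depend on them. The change is worth making because it is cheap, and cheapest before the core-lab data points are fixed.

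**What to change.** 1. Define embolization to a distal or new territory in the protocol, so that sites and the core lab apply the same criterion.
2. Add it to the specific adverse events as a yes/no entry for each procedure, with vessel and pass number.
3. Add it to the blinded core-lab read at the three existing time points (after the first pass, after the final aspiration pass, at the end of the procedure), with a not-assessable category, before the Reading Guidelines are approved.
4. Report it by assigned arm with a 95% confidence interval, as a descriptive safety outcome without a claim of power, and supply it to the DSMB.

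**Cost.** One CRF field and one item on a reading form, for angiograms that are already submitted and scored. No added imaging, visit or treatment change is needed. Core-lab item 1f warns that database changes after the website is launched may need revalidation and incur fees, which is a further reason to make the change now.

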The primary endpoint is the first pass effect (FPE), defined as TICI 2c or 3 after the first attempt of direct aspiration thrombectomy, as determined by core lab assessment. The rate of successful FPE will be compared between the Plunger group and the static aspiration group per the mITT population as above.

Null hypothesis: the rate of successful FPE is not different between static and plunger aspiration. The rate of FPE will be compared between the two groups by chi-square analysis. If there is a significant difference between the two, then the null hypothesis will be rejected.

Analysis of primary safety endpoint

The primary safety endpoint is the rate of sICH at 24 hours compared between the static and Plunger aspiration groups. A chi-square test will assess for differences in rate of sICH between the two treatment groups in the mITT population. Secondary analyses will account for ASPECTs score and time to treatment between the two groups.

Analysis of secondary endpoints

Overall rate of TICI 2b or 3 recanalization with Plunger vs. static aspiration will also be compared using chi-square analysis on the mITT population.

For the following additional binomial secondary efficacy endpoints, treatment groups will be compared using logistic regression models as appropriate:

- Rate of successful navigation of aspiration catheter to clot
- Rate of rescue treatment with stent-retrievers
- Rate of complete clot ingestion
- Rate of recanalization by clot density on CT (hyperdense vs isodense)

The 90-day functional outcomes, including mRS and PROMIS-10, will be compared between the two groups using ordinal shift analysis.

Randomization

Patients will be randomized (1:1; permuted block randomization) once the decision is made for patient to go for thrombectomy using the REDCap randomization tool.

Adverse events

Throughout the course of the clinical investigation, all adverse events will be recorded on the applicable Adverse Event CRF. The date of onset, date of resolution, severity, and action taken will be evaluated by the Investigator. The relationship to the technique or device, relationship to the procedure, and clinical significance will be evaluated. The neurological outcomes and adverse events will be reported.

Adverse Event Classification and Definitions

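### The adverse event relatedness list has no 'not related' level, two overlapping codes and no consistent place for device, which blurs descriptive attribution but not the primary safety comparison

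*Protocol*

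**What the plan says.** The protocol asks for a causality judgment in two places. The Adverse events section states: "The relationship to the technique or device, relationship to the procedure, and clinical significance will be evaluated". Event Reporting Requirements asks the investigator to assess "the relationship of each adverse event to the procedure or device".

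The codes for that judgment are under Relatedness in Adverse Event Assessments. There are three:

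- The first code reads: "Procedure-related: Event has a strong temporal relationship to the study procedure". The definition continues: "This includes AEs attributable to any device(s) used at procedure, such as access devices", followed by further examples of devices.
- The second code reads: "Technique-related: Event has a strong temporal relationship to the use of aspiration for thrombectomy".
- The third code, for whatever is left over, reads: "Unknown: Event relationship cannot be attributed to any of the above categories and remains undetermined".

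The scope of collection is wide. Adverse Event Classification and Definitions counts any untoward occurrence, "whether or not related to the investigational procedure". Event Reporting Requirements covers "events occurring from the point of consent until a subject exits the study", and the Schedule of assessments lists adverse events at the procedure, at 24 hours and at the 90-day telephone contact.

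**The concern.** The codes do not match the judgments that the protocol asks for. An investigator who is satisfied that a late event has nothing to do with the thrombectomy has no code that says so. An investigator who sees an event during aspiration has two codes that fit and no rule for using them. An investigator who blames a device has no device code and finds the device question framed differently from one section to another.

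At stake is how far the attribution data can be read. The trial's objective covers the safety as well as the efficacy of two aspiration techniques, so readers will look at which events were ascribed to technique. If the unknown column mixes unrelated with undetermined events, and the technique and procedure columns are filled by differing local habits, those tables say little. This is settled when the site enters the data. An analysis plan cannot restore a distinction that was never collected.

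**Working it through.** No arithmetic applies: the point depends on no rate, effect size, alpha or sample size, and the protocol gives no expected number of adverse events. The check sets the required judgments beside the available codes.

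**1. An event judged unrelated.** The definition of an adverse event includes such events ("whether or not related to the investigational procedure"), and collection runs to study exit, so they must be recorded. Neither the procedure nor the technique code fits. The unknown code sets two conditions: the event fits neither of the other codes, and its relationship is undetermined. An event judged unrelated meets the first but not the second. Read strictly, it has no code. In practice unknown is the only one left, and there it sits beside events whose cause is truly uncertain.

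**2. An event during aspiration.** The procedure code asks for a strong link in time to the study procedure, and the technique code asks for the same link to aspiration. Aspiration is a step of the procedure, so an event close in time to aspiration meets both. The protocol gives neither an order of precedence nor a statement that both may be recorded.

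**3. An event ascribed to a device.** Three places treat it as follows:

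| Place in the protocol | Device is grouped with | Treated separately or omitted |
|---|---|---|
| Adverse events | technique | procedure is a separate judgment |
| Event Reporting Requirements | procedure | technique is not mentioned |
| Adverse Event Assessments, Relatedness | procedure (device events sit inside that code) | technique is a separate code |

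A device event therefore does have a code, namely procedure-related. What cannot be recorded is device-relatedness as distinct from procedure-relatedness.

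**4. What depends on these codes.** The primary safety endpoint is symptomatic intracranial hemorrhage at 24 hours, defined by new hemorrhage on CT with a worsening of 4 or more NIHSS points. It is compared between arms by chi-square. Relatedness enters neither the definition nor the test, and no analysis described in the protocol uses counts of technique-related events. The consequence is limited to descriptive attribution.

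**The case against.** The strongest reply is that this is a drafting gap with little effect, and much of that reply stands.

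- **The safety comparison is untouched.** A reader might infer that the trial's safety conclusion depends on these codes. The protocol does not support that: hemorrhage is compared by arm without attribution, and all adverse events can be compared by arm whatever code they carry.
- **Some of the information can be recovered.** Vessel perforation and dissection, the likeliest events to meet both definitions, require detailed narrative reports. Date of onset, severity and action taken are recorded for every event. It would be too strong to say that the distinction is lost for good. Recovery is weaker for events with no required narrative.
- **Nothing says that only one code may be chosen.** A reader might infer that an operator who knows the assigned technique must pick one code and could do so differently by arm. The protocol gives the evaluation to the investigator, does not call the codes mutually exclusive, and lists the technique-or-device and procedure relationships as separate judgments. Differential coding is possible but not shown, and the protocol offers no figure for its size.
- **The procedure code is not purely about timing.** Its device clause speaks of events attributable to a device.
- **The eCRF is not shown.** It may hold more options. If so, it departs from the protocol's list, and the two still need to be aligned.

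The reply does not dispose of three facts: the list has no unrelated level, it does not say how overlapping codes are to be used, and device is placed differently across sections.

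**Conclusion.** The point holds as a minor defect in the coding of causality. Events judged unrelated have no code of their own and would be filed as undetermined; the procedure and technique codes overlap for events during aspiration; and device-relatedness cannot be recorded distinctly.

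A reader might go further and conclude that the required relatedness cannot be recorded at all. That is not so: a positive link to the procedure (devices included) or to the technique can be coded.

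The size of the effect cannot be put in numbers from the protocol. It is confined to descriptive attribution tables, and no type I error, power or sample-size figure changes. The conclusion assumes that the eCRF follows the protocol's three-code list.

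**What to change.** Revise the Relatedness paragraph and the matching eCRF field:

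1. Add an explicit 'not related' level, and keep unknown for events whose relationship is truly undetermined.
2. Rate the relationship to technique, to device and to procedure separately, and state that more than one may apply.
3. Base each rating on causal plausibility as well as timing.
4. Reconcile the device wording in Adverse events, Event Reporting Requirements and the Relatedness list, and name technique wherever relatedness is required.
5. State that adverse events will be compared by assigned arm regardless of attribution, with attribution shown as a supporting table.

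The cost is one protocol paragraph, an eCRF field change and minor site retraining, with no added visits or staff. It is cheapest before enrollment begins, because events already coded would have to be reviewed again.
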